3.7 Collection of Clinical Specimens

The following clinical specimens are required to be collected from subjects in this study:

- Blood at Days 1, 22, 181, and 271.
- Urine at Day 1 for females of childbearing potential.

Processing of each specimen should be completed by a qualified site member and in accordance with the study-specific Clinical Specimen Laboratory Manual. Testing of clinical specimens will be performed by a Seqirus or designated laboratory. Refer to the study-specific Clinical Specimen Laboratory Manual for additional details.

Blood Specimens

Approximately 10 mL sample of blood will be drawn from all subjects at Visit 1 (Day 1) before vaccination, and at Visit 3 (Day 22), Visit 5 (Day 181), and Visit 6 (Day 271). The blood volume will not exceed 10 mL at each time point in order to provide the necessary serum volume (approximately half of the blood draw volume) for the serology assays.

The blood will be used for immunological assays. See [Section 7, Assessments](#) for additional details.

The total amount of blood collected over the study period per subject will be 40 mL.

Protocol Number: V118_23

Product Name: aQIV

Document Status: Final Version 3.0, Document Date: 11 Jul 2022

In addition, approximately 50 subjects at selected sites may be asked to voluntarily provide extra blood samples of 50 mL at Day 1 and 50 mL at Day 22 that can be used for future research not directly related to this study, but with the purpose to improve the understanding of the influenza vaccines or disease. If subject agrees to provide extra blood samples, it will be at the discretion of the investigator to decide whether the subject is eligible to provide extra blood samples.

Urine Specimens

Urine will be collected for pregnancy testing in females of childbearing potential. Urine will be collected at Visit 1 (Day 1) before vaccination.

3.8 Stopping/Pausing Guidelines

There are no predetermined stopping rules in this study. Subjects may be withdrawn from the study according to investigator discretion as described in [Section 4.5, Premature Withdrawal from Study](#).

3.9 Data Monitoring Committee

Not applicable.

3.10 End of Study

Most clinical trials intended to support the efficacy and safety of an Investigational Product proceed to full completion of planned sample size accrual.

Evaluation of the primary and secondary immunogenicity objectives requires the testing of biological samples from the study subjects, which can only be completed after all of the samples for these objectives are collected. The last samples for the analysis of the secondary objectives will be taken at Visit 5 (Day 181). The last clinical assessment for the secondary safety objective will be at Visit 6 (Day 271). Accordingly, for the purpose of this protocol, end of study is defined as the completion of the testing of the Visit 5 (Day 181) biological samples, to be achieved no later than 8 months after collection of the last biological sample at Visit 5 (Day 181), or the Last Subject Last Visit, whichever is later. The local end of the study is defined as the Last Subject Last Visit within the country.

4 SELECTION OF STUDY POPULATION

4.1 Inclusion Criteria

In order to participate in this study, all subjects must meet ALL of the inclusion criteria described.

1. Individuals 50 to 64 years of age (i.e. 50 to \leq 64 years) on the day of informed consent;
2. Individuals who have voluntarily given written consent after the nature of the study has been explained according to local regulatory requirements, prior to study entry;
3. Individuals who can comply with study procedures including follow-up⁹;
4. Males, females of non-childbearing potential¹⁰ or females of childbearing potential who are using an effective birth control method¹¹, at least 30 days prior to informed consent, which they intend to use for at least 2 months after the study vaccination.

4.2 Exclusion Criteria

In order to participate in this study, all subjects must not meet ANY of the exclusion criteria described below:

1. Females of childbearing potential who are pregnant, lactating, or who have not adhered to a specified set of contraceptive methods from at least 30 days prior to study entry and who do not plan to do so until 2 months after the study vaccination;
2. Progressive, unstable or uncontrolled clinical conditions;

⁹ A subject is considered to be compliant if the investigator judges that the subject will complete the Subject eDiary, will be available for all the follow-up visits and for the telephone calls as scheduled in the study.

¹⁰ A female is considered to be of non-childbearing potential prior to menarche and after natural or induced menopause. Natural menopause is recognized to have occurred after 12 consecutive months of amenorrhea for which there is no other obvious pathological or physiological cause. Induced menopause is recognized to have occurred after hysterectomy, after bilateral oophorectomy, or iatrogenic ablation of ovarian function.

¹¹ The following birth control methods are considered effective: abstinence, hormonal contraception (such as oral, injection, transdermal patch, implant) if used for at least 30 days prior to informed consent, diaphragm with spermicide, tubal occlusion device, intrauterine device, tubal ligation, male partner using condom with spermicide, male partner having been vasectomized at least six months prior to informed consent.

Protocol Number: V118_23

Product Name: aQIV

Document Status: Final Version 3.0, Document Date: 11 Jul 2022

3. Hypersensitivity, including allergy, to any component of vaccines, medicinal products or medical equipment whose use is foreseen in this study;
4. History of any medical condition considered an AESI (see [APPENDIX 2 – List of Adverse Events of Special Interest](#));
5. Known history of Guillain Barré syndrome or another demyelinating disease such as encephalomyelitis and transverse myelitis;
6. Clinical conditions representing a contraindication to intramuscular vaccination and blood draws;
7. Abnormal function of the immune system resulting from:
 - a. Clinical conditions;
 - b. Systemic administration of corticosteroids (PO/IV/IM)¹² at a dose equivalent to ≥20 mg/day of prednisone for more than 14 consecutive days within 90 days prior to informed consent. Topical, inhaled and intranasal corticosteroids are permitted. Intermittent use (one dose in 30 days) of intra-articular corticosteroids is also permitted;
 - c. Administration of antineoplastic and immunomodulating agents or radiotherapy within 90 days prior to informed consent;
8. Received immunoglobulins or any blood products within 180 days prior to informed consent;

¹² PO= by mouth; IV=intravenous; IM= intramuscular

9. Received an investigational or non-registered medicinal product within 30 days prior to informed consent, or who are unwilling to refuse participation in another clinical study at any time during the conduct of this study (notes: i. concomitant participation in a study not involving or no longer involving administration of drugs, vaccines, or medical devices, is acceptable (e.g. studies in safety follow-up phase, observational studies); ii. concomitant participation in a COVID-19 vaccine study is acceptable provided that the vaccine dosing interval mentioned in Exclusion Criterion #11 is adhered to);
10. Receipt of any influenza vaccine within 6 months prior to enrollment in this study, or plan to receive influenza vaccine during the study period;
11. Receipt of any (investigational or licensed) COVID-19 vaccine within 14 days (non-replicating vaccines) or 28 days (replicating vaccines) prior to enrollment or plan to receive any COVID-19 vaccine within 7 days from study vaccination;
12. Receipt of any inactivated non-influenza vaccine within 14 days or live-attenuated vaccine within 28 days prior to enrollment in this study or plan to receive any other non-influenza vaccine within 28 days from study vaccination;
13. Acute (severe) febrile illness (See [Section 4.3, Criteria for Delay of Vaccination](#));
14. Any other clinical condition that, in the opinion of the investigator, might interfere with the results of the study or pose additional risk to the subject due to participation in the study;
15. Study personnel or immediate family members or household member of study personnel.

4.3 Criteria for Delay of Vaccination

There may be instances when individuals meet all eligibility criteria for vaccination yet have a transient clinical circumstance, such as an infection, which may warrant delay of vaccination: body temperature elevation ($\geq 38.0^{\circ}\text{ C}$ [$\geq 100.4^{\circ}\text{ F}$]) within 3 days prior to intended study vaccination], or prophylactic use of antipyretics and/or analgesic medications within 24 hours prior to vaccination. Under such circumstances, a subject may be considered eligible for study enrollment after the appropriate window for delay has passed and inclusion/exclusion criteria have been rechecked, and if the subject is confirmed to be eligible.

4.4 Criteria for Repeat Vaccination in the Study

Not applicable.

4.5 Premature Withdrawal from Study

Subjects may withdraw at any time or be withdrawn from the study at the discretion of the investigator should any untoward effects occur and/or for safety reasons. In addition, a subject may be withdrawn by the investigator or the Sponsor if he/she violates the study plan or for administrative reasons. The investigator or study coordinator must notify the Sponsor immediately when a subject has been withdrawn due to an AE.

The circumstances above are referred to as premature withdrawal from the study, and the reason for premature withdrawal should be clearly documented and detailed in the source documentation. The investigator should make every attempt to evaluate the subject's safety, including resolution of ongoing AEs, at the time of premature withdrawal. If a subject wants to withdraw from the study prior to the last planned study visit, the subject will be asked to be followed for safety for the duration of the study. When a subject withdraws, or is withdrawn, from the study, the procedures described in [Section 5.6.1, Early Termination Visit](#) should be completed if possible.

Any subject who becomes pregnant during the study, despite the protocol requirement for adequate contraception, should be encouraged to continue participating in the study for safety follow-up. The site must record a confirmation of pregnancy in the eCRF and must complete a Pregnancy Reporting/Outcome Form as soon as possible after learning of pregnancy occurrence (see [Section 7.1.6, Pregnancies](#) for further details). If the pregnant subject withdraws from the study for any of the below categories except death, the site will obtain permission from the subject to continue to remain in contact with her until the outcome of the pregnancy is known, even if the outcome is not known until after the subject reaches the end of the follow-up period.

The reasons for premature withdrawal from the study include: AE, death, withdrawal of consent, lost to follow-up, and protocol deviation. These reasons are described in greater detail below.

Adverse Event

For any subject withdrawn from study participation prior to the planned Study Completion Visit, it is important to determine if an AE was associated with the reason for discontinuing the study. This AE must be identified on the AE eCRF page by indicating "Withdrawn from study due to AE". Any ongoing AEs at the time of study withdrawal must be followed until resolution or stabilization.

Death

For any subject withdrawn from study participation due to death, this should be noted on the Study Completion eCRF page and the associated SAE that led to the death must be reported.

Withdrawal of consent

The subject can withdraw consent for participation in the study at any time without penalty or loss of benefit to which the subject is otherwise entitled. Reason for early termination should be deemed as “withdrawal of consent” if the subject withdraws from participation due to a non-medical reason (i.e., reason other than AE). If the subject intends to withdraw consent from the study, the investigator should clarify if the subject will withdraw completely from the study or if the subject will continue study participation for safety, or a subset of other study procedures. If the subject requests complete withdrawal from the study, no further study interventions will be performed with the subject.

Lost to Follow-Up

For subjects who fail to show up for planned visits (clinic or telephone contacts), study staff are encouraged to make at least three documented attempts to contact the subject by telephone and at least one documented written attempt to contact the subject to encourage the completion of study termination procedures. These efforts to contact the subject should be recorded in the source document. The termination date for the subject to be captured on the Study Completion eCRF page is the date of the last successful contact (clinic visit or telephone) with the subject.

Other Reasons

Examples for subjects withdrawn from the study due to an “other” reason can include: Sponsor decision to terminate the study, subject meeting a prespecified withdrawal criterion, subject discontinuation for insurance issues, moving, no time, etc. This reason should be noted in the Study Completion eCRF page and any ongoing AEs at the time of study withdrawal must be followed until resolution/stabilization.

Study Terminated by Sponsor

If the clinical study is prematurely terminated by the Sponsor, the investigator is to promptly inform the study subjects and local Ethics Committee (EC)/Institutional Review Board (IRB) and should assure appropriate therapy and follow up for the subjects. All procedures and requirements

pertaining to the archiving of study documents should be followed. All other study materials (study medication/vaccines, etc.) must be returned to the Sponsor.

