7 ASSESSMENTS

7.1 Safety Assessments

The measures of safety used in this study are routine clinical procedures. They include a close vigilance for, and stringent reporting of, selected local and systemic AEs routinely monitored in vaccine clinical studies as indicators of reactogenicity.

An AE is defined as any untoward medical occurrence in a clinical investigation subject administered a pharmaceutical product at any dose that does not necessarily have to have a causal relationship with this treatment; therefore, an AE can be any unfavorable and unintended sign (including an abnormal laboratory finding, for example), symptom, or disease temporally associated with the use of an investigational product, whether or not considered related to the investigational product. This definition includes intercurrent illnesses or injuries and exacerbation of pre-existing conditions.

The period of observation for AEs extends from the time immediately after the subject has received the study vaccine until he or she completes the study completion visit (Day 271) or terminates the study early. Events occurring after the informed consent form is signed but prior to receiving study vaccine will be documented as medical history in the source document and medical history eCRF.

Adverse events are collected as either solicited or unsolicited AEs. Solicited events are derived from organized data collection systems, such as Subject eDiaries or interview.

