8.3.4 Full Analysis Set (FAS) Immunogenicity

Full Analysis Set Immunogenicity

All subjects in the All Enrolled Set who are randomized, received study vaccination and provide immunogenicity data at any time point.

In case of vaccination error, subjects in the FAS sets will be analyzed "as randomized" (i.e., according to the vaccine the subject was designated to receive, which may be different from the vaccine the subject actually received).

The FAS Immunogenicity will be used for immunogenicity superiority comparisons.

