4.1.1 Definition of Randomization/Vaccination Errors

The list below provides categories for errors that may occur during randomization and/or vaccination.

Randomization errors:

- Administered wrong kit (Subject received vaccine from a kit different from the kit number that was assigned at randomization).

Vaccination errors:

- Administered only part of the study vaccine.
- Incorrect vaccine administration (e.g. incorrect location or route)
- Administered expired vaccine.
- Administered temperature deviated vaccine.

Stratification error:

- Subject randomized in the wrong stratification stratum.

Differentiate between incorrect stratification and randomization errors.

A randomization error is defined as a subject receiving a vaccine from another kit than the one assigned by randomization. If after unblinding, it appears that the vaccine from the incorrect kit is identical to the vaccine from the assigned kit, the error will be reported as a major protocol deviation (PD), but the data from the subject will not be excluded from any analyses sets. If the vaccine is different from the vaccine in the assigned kit, the randomization error is a Clinical Study Report (CSR) - reportable PD and the subject's data should be analyzed as randomized in Full Analysis Set (FAS), excluded from Per Protocol Set (PPS) and analyzed as received for Safety.

Incorrect stratification is defined as enrollment and randomization of a subject based on incorrect stratification information at baseline. Incorrect stratifications should be split for major and minor errors.

- Major stratification errors are those resulting in administration of incorrect dosage or schedule, not corrected on time, i.e. not corrected before administration of the vaccine. These will be handled as CSR-reportable PD.
- Minor stratification errors are those not having impact on dose/schedule administered. These will not be considered as CSR reportable PD.

Since the vaccine dosage and regimen in this study are independent from the stratification factors, major stratification errors are not applicable. In the analysis of covariance (ANCOVA) and in the subgroup analyses, subjects will be analyzed according to their actual age and/or influenza vaccination history.

Stratification error	FAS	PPS	Safety Sets All-Enrolled Set All-Exposed Set
Minor	Analyze as corrected	Analyze as corrected	Analyze as corrected
Major*	Analyze as originally stratified	Exclude from analysis	Analyze as corrected

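### Section 4.5 lets vaccinated subjects be withdrawn for deviations or administrative reasons, which can cost later titers and safety follow-up that the analysis plan means to keep

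*Protocol*

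**What the plan says.** Protocol Section 4.5 gives the investigator and the sponsor a discretionary power: "In addition, a subject may be withdrawn by the investigator or the Sponsor if he/she violates the study plan or for administrative reasons". No time limit is attached, and the only vaccination is on Day 1. The same section states: "The reasons for premature withdrawal from the study include: AE, death, withdrawal of consent, lost to follow-up, and protocol deviation". Paragraphs follow on adverse events, death, consent, loss to follow-up, other reasons and termination by the sponsor. None describes protocol deviation.

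On what happens next, Section 4.5 distinguishes who made the decision. "If a subject wants to withdraw from the study prior to the last planned study visit, the subject will be asked to be followed" up on safety until the study ends; this is written for the subject who chooses to leave. For both kinds of departure, "When a subject withdraws, or is withdrawn, from the study, the procedures described in" Section 5.6.1 are to be carried out if possible, and "Any ongoing AEs at the time of study withdrawal must be followed until resolution or stabilization". Protocol Section 7.1 runs the AE observation period from vaccination "until he or she completes the study completion visit (Day 271) or terminates the study early".

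The analysis sections treat deviations differently:
- Protocol Section 8.3.8 has a deviation remove data from an analysis set when the analysis is done.
- Protocol Section 8.3.5 and SAP Section 7.4 exclude deviators from the PPS.
- SAP Section 4.1.1 keeps a subject who received the other vaccine in the FAS as randomized and in the safety sets as received.
- SAP Section 4.2 keeps unblinded subjects in the FAS and safety sets.
- Missing titers are handled by complete-case analysis (Protocol Section 8.4.2.3.3, SAP Section 8.2), and the protocol rules out imputation.

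**The concern.** With one dose on Day 1, withdrawing a vaccinated subject for a deviation or an administrative reason prevents no study exposure. Its effect is on data collection. The FAS carries objectives 1b, 2a and 2b and supports 1a, and its rules are written so that deviators stay in. They can contribute only if their later sera are drawn.

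The loss is also selective. It follows from a discretionary decision made after randomization and is linked to the subject's conduct, while both documents treat missing titers as missing completely at random. SAP Section 8.2 considers a sensitivity analysis only when more than 10% of subjects have missing data. The planned drop-out is itself 10%, so a small selective loss inside it would not prompt one.

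On safety, SAEs, AESIs and AEs leading to withdrawal are a secondary endpoint through Day 271 (Protocol Section 8.1.2.1). A subject who chooses to leave is asked to stay under safety follow-up; a subject removed by the investigator or sponsor is not. The protocol gives no reason for the difference.

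**Working it through.** **1. Set membership after withdrawal.** The FAS needs randomization, vaccination and an immunogenicity result at any time point (Protocol Section 8.3.4, SAP Section 7.3). Blood is drawn from every subject after randomization and before vaccination (Protocol Section 5.1.5). A vaccinated subject with a Day 1 result is therefore in the FAS whatever happens later. The safety sets need exposure and some AE data (Protocol Section 8.3.3); withdrawal is not an exclusion.

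**2. What is lost, by time of withdrawal.** The GMT model uses the Day 22 or Day 181 titer as outcome, with complete cases only. Nominal visit days are used and visit windows are ignored.

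| Withdrawn | In FAS | Day 22 titer (1b, 2a, FAS support for 1a) | Day 181 titer (2b) | Days of new SAE/AESI collection no longer assured |
|---|---|---|---|---|
| Before Day 22 draw | yes | missing | missing | more than 271 − 22 = 249 |
| Between Day 22 and Day 181 draws | yes | present | missing | between 271 − 181 = 90 and 249 |
| After Day 181 draw | yes | present | present | fewer than 90 |

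**3. The plan's own sample size.** Inputs from Protocol Section 8.5: A/H1N1 difference δ = 0.07 log10, SD σ = 0.46, one-sided alpha 0.025, power 90%, ratio 1:1, drop-out 10%.

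n per arm = 2(z0.975 + z0.90)²(σ/δ)² = 2 × (1.960 + 1.282)² × (0.46/0.07)² ≈ 908, so 1,816 evaluable. 1,816/0.90 = 2,018. Both figures are reproduced; power at 908 per arm is 90.0%. The B row is also reproduced (496 and 552). A/H3N2 gives 232 and 258 against the stated 234 and 260, which is immaterial here.

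**4. Power under extra loss.** The documents give no rate for these withdrawals, so the extra loss e before Day 22 is an assumption. n per arm = 2,018 × (0.90 − e)/2, and power = Φ(δ/(σ√(2/n)) − 1.960).

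| Extra loss e | Evaluable | A/H1N1 superiority power |
|---|---|---|
| 0% | 1,816 | 90.0% |
| 1% | 1,796 | 89.7% |
| 2% | 1,776 | 89.4% |
| 5% | 1,715 | 88.3% |
| 10% | 1,614 | 86.4% |

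A/H3N2 and B stay at about 100%. Power for at least 2 of 4 strains stays above 99.9% throughout (strains taken as independent).

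**5. Possible bias.** Suppose a fraction f of one arm is lost and its mean log10 titer differs by D from those retained. The retained mean then differs from the full-arm mean by f × D. With f from 1% to 5% and D from 0.1 to 0.3 (both assumed), the shift is 0.01 × 0.1 = 0.001 to 0.05 × 0.3 = 0.015. The GMT ratio changes by a factor of 10^0.001 = 1.0023 to 10^0.015 = 1.0351, or 0.2% to 3.5%. Against the assumed A/H1N1 difference of 0.07, a middle case (f = 2%, D = 0.2) gives 0.004/0.07 = 6%, and the extreme corner 0.015/0.07 = 21%. Equal f and D in both arms would cancel.

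**The case against.** The best defence is that the clause is permissive and that the documents already contain the damage.

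- The text says a subject may be withdrawn, and nothing directs sites to withdraw deviators.
- Investigators are blinded (Protocol Section 3.5), which limits arm-related choices.
- The early-termination procedures point to Protocol Section 5.6, which includes an SAE and AESI interview and a blood draw, although a note to Table 0-1 asks early leavers only for the safety-related procedures.
- Ongoing AEs are followed, and a later SAE thought to be caused by the vaccine must still be reported (Protocol Section 7.1.5.1).
- Study withdrawals (SAP Section 9.1) and blood draws by visit (SAP Section 11.1) are tabulated by vaccine group.
- An absolute bar on administrative withdrawal would not work if a site closed.

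Most of this stands, and it limits the size of the problem. It does not remove it. Protocol Section 5.6.1 ends participation once the completion page is filled in, and no text requires collection of new events after that for a subject who was withdrawn. An early-termination sample is not a Day 22 or Day 181 sample unless it happens to fall in that window, and neither document says how such a titer would enter those analyses. Tabulation shows the loss but does not prevent it. The point about site closure is accepted and is met in the fix.

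**Conclusion.** The concern holds in a narrow form. Section 4.5 permits withdrawal after vaccination on grounds that the analysis plan handles by PPS exclusion. The subject remains a member of the FAS and safety sets, but Day 22 or Day 181 titers can be missing and new SAE/AESI collection can stop early. The frequency is unknown. The effect on power and on the GMT ratio is probably small under the assumptions shown, so the case rests on selective missingness and shortened safety follow-up that could be avoided.

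Four stronger inferences are not supported:
- A reader might infer that these subjects leave the FAS or the safety sets. The set definitions keep them in, and one withdrawn after the Day 22 draw still counts for 1b, 2a and the FAS support for 1a.
- A reader might infer that the FAS turns into a per-protocol set. That would need sites to withdraw most deviators before Day 22, and nothing suggests they would.
- A reader might take the subject given the wrong vaccine as the typical case. SAP Sections 4.1.1 and 6.2 settle that error after unblinding, so a blinded investigator would not normally know of it by Day 22. Protocol Section 6.4 on administration errors does not mention withdrawal.
- A reader might infer a threat to the sample size. The calculations do not show one.

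**What to change.** In Protocol Section 4.5:
- State that after vaccination a protocol deviation, or an administrative reason concerning an individual subject, does not by itself end participation. The deviation is recorded and handled through analysis-set exclusion. Scheduled sera and safety contacts continue to Day 271 unless the subject withdraws consent or the study or site closes.
- Extend the offer of safety follow-up to the end of the study to subjects withdrawn by the investigator or sponsor.
- Describe protocol deviation as a withdrawal reason, or delete it from the list.
- Leave the text on withdrawal for safety reasons as it is.

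If follow-up is already complete, the clinical study report should list investigator and sponsor withdrawals after vaccination by arm, reason and timing relative to Day 22 and Day 181.

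The cost is protocol wording, any matching change to the completion page, and continued visits for what should be a few subjects. The sample size and the analysis model do not change.
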